15.5 Enrollment/Stratification/Randomization

This is a randomized trial. Trial randomization will be computer-generated by the study's central data manager at Johns Hopkins University School of Medicine. Eligible patients who meet all of the inclusion criteria and none of the exclusion criteria will be randomized in a 1:1 ratio to the study arms. Contacts of the same index case will be considered a cluster and assigned to the same treatment arm according to the randomization of the first enrolled contact. Cluster (contacts of an index patient) size is limited to 2 participants per index case due to the diminishing returns in terms of power per enrollee within a household.

Randomization will be stratified by study site. After household contacts have signed informed consent forms, they will be randomized as a cluster to the same study arm, i.e. all receiving the same regimen. Other household members subsequently identified will not be eligible for the study.

The study is unblinded for practical reasons owing to differing pill counts between the arms and adherence being essential to the primary outcome.

15.6 Maintaining Trial Treatment Randomization Codes

The Johns Hopkins data manager will create a randomization sequence using STATA.

To prevent selection bias in the assignment to treatment the allocation sequence will be concealed from those assigning participants to intervention groups, until the moment of assignment.

15.7 Participant Enrollment and Follow-up

See Section 12.1.3

15.8 Data and Safety Monitoring

A Data and Safety Monitoring Board (DSMB) will review the study protocol and oversee progress of the trial at least annually. DSMB representatives will be determined by JHU who will manage the DSMB, but will include an independent statistician and at least one clinician who is experienced in the field of TB care.

The DSMB will meet at the following time points: Organizational Meeting, scheduled review meeting for interim analysis, annually, ad hoc meeting to address a specific safety concern, and a final meeting.

15.8.1 Planned Interim Analysis and Stopping Guidelines

After 25 participants in Arm A have completed 4 weeks treatment (28th HP dose), and 25 participants from ARM B have completed 4 weeks treatment (their 4th HP dose), we will conduct an interim safety and adherence assessment to ensure that 1HP is safe and well tolerated by HIV-negative participants, as compared with 3HP.

No early stopping rules will be formally adopted for this Phase IV trial.

Enrollment will not pause during the interim analysis. However, when participants from 80 households have completed 16 weeks on-study, a masked assessment of the within-household correlation will be made to verify sample size assumptions.

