7.2 Rationale

With support from the NIH and the CDC, we have pioneered the development of short-course, rifamycin-based TB preventive therapy (TPT) over the past 15 years. We have evaluated the efficacy of 3 months of weekly rifapentine and isoniazid (3HP) in people with and without HIV infection and showed that it is non-inferior to longer courses of INH, with better adherence and less toxicity. (Schechter 2006; Martinson 2011; Sterling 2011)

This regimen is now recommended as a first-line treatment for latent TB infection by the CDC and the World Health Organization, offering the potential of substantially increased uptake of TPT as part of the END TB Strategy. (WHO 2018)

More recently, supported by NIAID, we have shown that one month of daily rifapentine and isoniazid (1HP) is non-inferior to nine months of INH in people with HIV infection. (Swindells 2019) The availability of two innovative, new short-course TPT regimens offers a transformative opportunity to global TB control and achieving the End TB targets. However, a major question still requiring evidence is the safety of the 1HP regimen in people without HIV infection.

While the efficacy of 1HP can be assumed from its success in HIV-positive people, safety cannot. In the 1990s, several studies supported by NIAID and the CDC showed that a 2-month TBT regimen of rifampin and pyrazinamide (2RZ) was safe and efficacious in HIV-infected individuals.(Halsey 1998; Gordin 2000) However, subsequent research funded by NIAID, and experience in clinical practice, demonstrated that 2RZ was not safe in HIV-uninfected people, with high rates of hepatotoxicity and a number of deaths.(Schechter 2006; CDC 2001) No explanation for the difference in safety in HIV-infected and –uninfected people has ever been found, but this experience underscores the importance of demonstrating safety and tolerability in all target populations of new regimens for TBT.

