9. FORMAL INTERIM ANALYSIS

No formal interim analysis for treatment success or safety is planned.

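### The one early safety look tied to exposure waits for 25 participants to reach their 28th 1HP dose, so it comes later the more often 1HP is stopped; the delay is small unless toxicity is severe

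*Protocol*

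**What the plan says.** Protocol 15.8.1 starts the look "After 25 participants in Arm A have completed 4 weeks treatment (28th HP dose"). The matching condition for the control arm is that "25 participants from ARM B have completed 4 weeks treatment (their 4th HP dose"). Both conditions must be met. The stated purpose is to "ensure that 1HP is safe and well tolerated by HIV-negative participants, as compared with 3HP". The same section says "No early stopping rules will be formally adopted for this Phase IV trial" and "Enrollment will not pause during the interim analysis".

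Protocol 15.8 lists the other board meetings: organizational, at least annual, ad hoc for a specific safety concern, and final. None is tied to an early number of exposed participants. The 80-household check in 15.8.1 concerns within-household correlation, not safety.

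SAP section 9 says "No formal interim analysis for treatment success or safety is planned" and does not describe the 15.8.1 assessment.

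Under Protocol 12.3.1, a participant taken off study treatment stays on study and continues follow-up visits.

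**The concern.** The trigger depends on the outcome under review. The toxicity sections (Protocol 14.2.1 to 14.2.5) withhold or stop study drug for the events the trial targets: gastrointestinal, cutaneous, hypersensitivity, fever and liver events. Participants with these events reach a 28th dose late or never. The more often this happens, the more people must start 1HP before the look falls due.

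That matters because of why the trial exists. Protocol 7.2 recalls that an earlier short regimen, judged safe in people with HIV, proved otherwise in people without it: "2RZ was not safe in HIV-uninfected people, with high rates of hepatotoxicity and a number of deaths". Unexpectedly high toxicity is the case the early look is meant to catch, and it is the case in which this trigger is slowest. With no stopping rule and no enrolment pause, a later look means more people exposed before the board sees a pooled table.

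**Working it through.** The figure of 25 per arm is given without derivation, so there is nothing to reproduce. The check is how the number of 1HP starters, and the calendar time, depend on the share who stop.

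**Inputs from the documents**
- Trigger: 25 per arm (Protocol 15.8.1).
- Reference rates: 3% targeted safety events in the earlier 1HP trial (15.4); 6% and 13% planning rates for targeted events or discontinuation (15.3). They are used here as a range for the share who stop before dose 28. That is an approximation, because not every event leads to stopping.
- Earlier toxic regimen (2RZ) in Brazilian household contacts: 10% adverse events, 94% completion (Table 2).
- Arm B dose 4 falls on day 21, since 12.1.4 places day 22 at 24 hours after it.
- 500 participants, enrolled from the second half of year 1 into year 4 (9.3).

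**Assumptions**
- The documents give no monthly enrolment rate. Taking 30 to 42 months gives 500/42 = 11.9 to 500/30 = 16.7 per month in total.
- Stopping rates of 30% and 50% are stress values without a source.
- 5% stopping in Arm B before dose 4.

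**Starters needed.** If a share p stops before dose 28, the number of starters needed for 25 completers is negative binomial with mean 25/(1 − p).

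| p | Mean starters | 90th percentile |
|---|---|---|
| 3% | 25/0.97 = 25.8 | 27 |
| 6% | 25/0.94 = 26.6 | 28 |
| 13% | 25/0.87 = 28.7 | 31 |
| 30% | 25/0.70 = 35.7 | 41 |
| 50% | 25/0.50 = 50.0 | 59 |

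The 94% completion in Table 2 for 2RZ also gives 25/0.94 = 26.6.

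**Delay, simple form.** At 36 months, each arm enrols 500/36/2 = 6.94 per month. At 13% the extra starters cost (28.7 − 25)/6.94, about 0.54 months; at 30%, 10.7/6.94 = 1.54 months; at 50%, 25/6.94 = 3.6 months.

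**Delay, both arms required.** The look also needs 25 in Arm B, so stopping in Arm A delays it only when Arm A is the slower arm. A simulation with 1:1 allocation, Arm A at 28 days, Arm B dose 4 at 21 days and the look at the later of the two arms was compared with the same rule counting all starters. Ranges span the three enrolment rates.

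| p in Arm A | Mean delay (months) | 1HP participants enrolled at the look |
|---|---|---|
| Starter trigger | – | 32 to 34 |
| 3% | 0.1 to 0.2 | 34 to 35 |
| 6% | 0.2 to 0.3 | 34 to 36 |
| 13% | 0.4 to 0.5 | 36 to 38 |
| 30% | 1.1 to 1.5 | 41 to 44 |
| 50% | 2.8 to 3.9 | 56 to 58 |

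The starter trigger gives a look at about 4.1 to 5.4 months of enrolment. Counting Arm B at 28 days instead of day 21, as the fix below does, puts that look slightly later and makes every delay slightly smaller.

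**Interruptions.** The simulation leaves these out. They push the 28th dose back further, and the documents differ on how far: 12.1.5 defines 1HP completion as 28 doses within 6 weeks, while 14.2.7 allows 8 weeks from enrollment after a suspension. Read strictly, the trigger also omits participants who finish with 25 to 27 doses, although they meet the dose count for treatment success.

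**The case against.** The strongest reply is that 15.8.1 sets a time and not a review population. A reader might infer that the board would see only the 25 completers, so that 1HP discontinuations are absent and adherence is complete by construction. The documents do not support that. Nothing in 15.8.1 restricts the data, discontinued participants stay on study, all Grade 2 or higher events are captured (13.2.1), and the analysis is by intention to treat from the first supervised dose (15.8.3; SAP 8). Once the look occurs, early stoppers' events can be in it. Detection at the look is not reduced either: at a 10% event rate, the chance of at least one event is 1 − 0.9^25 = 93% among 25 starters and 1 − 0.9^28 = 95% among 28. This reply stands.

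Second, there are backstops: ad hoc board meetings (15.8), 24-hour reporting of serious events (13.3.9), 72-hour reporting of Grade 3 or higher hepatitis or hypersensitivity (13.3.5), and the principal investigator's power to suspend (13.1). None waits for a 28th dose. This also stands. It lowers the stakes but does not replace a pooled comparison by arm.

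Third, a reader might object that a full 1HP course is set against 4 of 12 doses of 3HP. The section describes both arms as having 4 weeks of treatment, and similar elapsed time is a legitimate basis for an early tolerability check. No decision rule rests on it.

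Fourth, SAP 9 might seem to contradict the protocol. It excludes only a formal interim analysis, which is compatible with an informal look without stopping rules.

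What remains is the timing: the trigger moves with the toxicity it should detect.

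**Conclusion.** The point holds as a weakness in timing. The only early look tied to exposure is set by treatment completion in Arm A, so it comes later as 1HP toxicity rises. At 3% to 13% stopping, the cost is about 1 to 4 extra 1HP starters and roughly two weeks or less. At 30% it is about 11 extra starters and 1.1 to 1.5 months; at 50%, 25 extra starters and 2.8 to 3.9 months.

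The direction follows from the wording alone. The starter counts need only the stopping share. The calendar figures also rest on the assumed enrolment of 12 to 17 per month and 5% stopping in Arm B. The two high stopping rates are assumptions, and Table 2 offers no precedent for them: the earlier toxic regimen had 94% completion, in a directly observed trial that ended early.

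The documents do not support saying that the look hides toxicity or that it is the only protection. The change is worth making because it costs almost nothing and corrects the trigger where it would matter most.

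**What to change.** In Protocol 15.8.1, trigger the look when the first 25 participants in each arm reach 28 days after their first dose, whether or not they are still on treatment. State that the review covers every participant with at least one dose by the data cut, with discontinuations and their reasons listed by arm. The Arm A count then stays at 25 starters at any toxicity rate. A one-line reference in SAP 9 to this non-formal review would remove doubt about its status.

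The 6-week window in 12.1.5 and the 8-week window in 14.2.7 for 28 doses of 1HP must be reconciled with each other.

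The cost is wording only: no added visits, participants or data. Repeating the table for the board when the same 3HP participants reach week 12 is optional and would add one short report.

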15.8.2 Interim Efficacy Review

No interim analysis for efficacy is planned.

15.8.3 Analysis Plan

Analyses will be intention-to-treat for both primary outcomes of successful completion and safety. For the successful completion outcome, losses to follow up (at 4 weeks for Arm 1HP and 12 weeks for Arm 3HP) will be considered as unsuccessful; a sensitivity analysis will be conducted among those not lost in both arms as of 12 weeks. For the safety outcome as of 24 weeks, losses will be considered as failures (safety events).

For the primary outcomes, if fewer than 5% of failures occur in households with 2 or more failures, p-values will be calculated using Fisher's exact test, and 95% confidence intervals (CI) for risk differences will be calculated using the standard asymptotic formula.

Otherwise, within-household correlation will be accounted for using

generalized estimating equations with logit link (for p-value) or identity link (for risk difference CI) and exchangeable correlation structure. If there are convergence problems, a log link function will be used, with delta-method-constructed confidence intervals.

Incidence of active tuberculosis will only be assessed during six months following enrollment but will be evaluated as an exploratory outcome. Incidence will be compared using Kaplan-Meier estimates at 24 weeks and Greenwood's variance formula. This will be a sufficiently rare event that within-household correlation will be ignorable. Censoring will be at last study visit or death. As a sensitivity analysis, TB-free survival will also be analyzed.

TAM studies for the Ultra Curto study are designed to capture the amount of time needed to provide each unit of clinical and/or laboratory services to the patients. Sampling for TAM data collection will be stratified to ensure a broad coverage of visits by time of day, day of week, and time of year, plus inclusion of participants who require additional clinical evaluation (e.g., for side effects) so that the data represents a range of clinical operational conditions in our study setting. The data from TAM study will be analyzed and reported as unit time per 1) each discrete activity specified (clinical, laboratory, and treatment management) in Table 1 and 2) assessed as total health care staff person-time required (reported by types of personnel) for one patient throughout his/her LTBI care cascade (from initial diagnosis and clinical evaluations to treatment completion, inclusive of management of side effects). These time estimates will include both the direct (e.g. patient's face-to-face interaction with health care staff) and indirect (e.g. administrative efforts such as chart reviews and data reporting) efforts relevant for programmatic component of the patient event schedules of the Ultra Curto trial."

15.8.4 Economic Analysis Plan

The economic analysis plan will be submitted as a separate companion study to this main trial.

16. DATA HANDLING AND RECORDKEEPING

16.1 Data Management Responsibilities

Data handling and record keeping will be performed by the site, under the supervision of the site PI in accordance with procedures that are documented in the site's detailed Data Management Operations Manual.

Each participant will be assigned a unique study ID number. This number will be recorded on each data collection form and clinical specimen. Personally

identifiable information including names will not be used on data collection forms. All study records will be stored in locked files in a secure area and access will be limited to study personnel and designated regulatory personnel. All forms will be reviewed prior to data entry for accuracy, consistency, and completeness by designated study staff.

Statistical analysis will be done as a joint effort between JHU Investigators and the site PI, using JHU statisticians.

16.2 Essential/Source Documents and Access to Source Data/Documents

Appropriate records will be maintained for this trial, in compliance with ICH E6 GCP, and regulatory and institutional requirements for the protection of confidentiality of participants. Study records (source documents, signed informed consent forms, IRB/IEC correspondence and approval letters, and screening logs) will be kept in a secure location accessible only to authorized study staff. The following will have access to study records: members of the study team; IRBs that review the study, the Office of Human Research Protections, the US FDA, EMEA, the NIAID, and other local, US, and international regulatory entities. Authorized representatives of the Sponsor and regulatory agencies will be permitted to examine study records for QA reviews, audits, and evaluation of the study safety and progress.

Secure archives are available on-site for preliminary storage after study closure, before moving them to an off-site, secure storage facility. Study records will be maintained by the investigator following study discontinuation in accordance with all applicable NIH and local regulatory requirements in Brazil.

16.3 Quality Control and Quality Assurance

Sites will submit a detailed quality management plan prior to study-start. QC and QA will be conducted according to site-specific SOPs.

Data will be validated on entry, using range and consistency checks. Quality control procedures will include review of CRFs for completion and correctness and source data verification. The study will be monitored by internal and external monitors. The study site will provide direct access to all trial-related facilities, source documents, and reports for the purpose of monitoring and auditing by the Sponsor, and inspection by regulatory authorities. Following written procedures, study monitors will verify that the clinical trial is conducted and data are generated, documented (recorded), and reported in compliance with the protocol and the applicable regulatory requirements.

17. CLINICAL SITE MONITORING

Site Monitoring will be conducted to ensure that human subject protection, study procedures, laboratory procedures, study intervention administration, and data collection processes are of high quality and meet Sponsor, JHU, Health Department (Rio de Janeiro)/FMT(Manaus) and regulatory guidelines, and that the study is conducted in accordance with the protocol and site SOPs. Site monitoring will be performed according to details in a written monitoring plan.

The study will be monitored internally at regular intervals according to site specific SOPs. Westat will conduct periodic external monitoring.

The following will be monitored by internal and external reviewers:

100% Source Data Verification for all enrolled participants. For these participants, the following will be conducted:

- Informed Consent Form (ICF) review for 100% of participants.
- On-site source data verification (SDV) of source documents: paper source versus electronic Case Report Form (eCRF)
- Eligibility criteria (full eligibility will be assessed for 100% of enrolled participants)
- Review of randomization documentation and verification of correct treatment arm allocation
- Monitoring of Investigational Product (IP) accountability and pharmacy documentation for all enrolled participants.
- Monitoring of safety laboratory results, requisition forms and shipping documentation
- Verifying that all biological samples have been collected and stored (e.g. urine, blood, and dried blood spot samples) as per protocol
- Sites' pharmacies to review product storage and management

18. HUMAN SUBJECTS PROTECTIONS

18.1 Institutional Review Board/Ethics Committee

This protocol, the informed consent document (Appendix VI), and any subsequent modifications must be reviewed and approved by the IRB or Ethics Committee (s) (EC) responsible for overseeing the study.

18.2 Vulnerable Participants

18.2.1 Pregnant participants and fetuses

This trial excludes pregnant participants

18.2.2 Prisoners

This trial excludes prisoners and individuals with known impending incarceration.

18.2.3 Children

For potential participants under 18 years of age, the assent of the child as well as the written informed consent of the child's legal guardian will be required for enrollment in this study. The child will receive, in language appropriate to the age and maturity of the child, an explanation of the research procedures; a description of the risks, discomforts, or inconveniences that the child might experience; and assurance that the child can withdraw from the study at any time.

The assent process will be conducted by a study staff member who is experienced in consent and assent procedures, and in accordance with IRB/IEC requirements. All study participants age < 18 years will provide oral or written assent and written consent by the participant's legal guardian, in accordance with national and/or local IRB/IEC requirements.

Participants who reach age 18 will be consented on the adult ICF at their next visit.

18.2.4 Illiterate participants

Illiterate participants will be consented by a trained research team member in the presence of an independent adult third party witness who is chosen by the participant, and is not a member of the research team.

The participant will make her or his mark or thumbprint as signature, and the witness will sign in the informed consent document, noting date and time of signature.

18.3 Informed Consent

Informed written consent and assent, where applicable, using IRB-approved consent forms, will be obtained by trained study personnel prior to performing study-specific procedures. Potential participant's and/or their parent/guardian will receive information about risks and possible benefits of study participation, study objectives and procedures, potential toxicities, and the informed consent process.

Informed consent requires the signature or mark of the participant and/or parent/ guardian if the participant is under age 18 years. A copy of the signed and dated informed consent document will be offered to participants for their records.

The rights and welfare of the subjects will be protected by emphasizing that the quality of the participant's medical care will not be adversely affected if they decline to participate in this study, and that they may withdraw consent at any time. If the choice is made not to participate in the study, the patient will be referred to local sources of TB care.

18.3.1 Informed Consent Process

This study will be conducted according to the ethical principles set forth in the Declaration of Helsinki, ICH-GCP, and local regulatory requirements as applicable.

Only individuals who provide written informed consent will be enrolled in this study. Written informed consent is required before any study-specific procedures are performed.

In an area of the facility that preserves confidentiality, trained study staff will explain the conditions of the study including potential harms and benefits, the nature and timing of study procedures, alternatives to study participation, that study participation is voluntary, that a decision to not participate in the study will not affect the quality of their future medical care, and that they may withdraw from participation at any time. The information in the Informed Consent document will be translated into relevant local languages.

Literate individuals will be provided with a language-appropriate document to read; illiterate individuals (i.e. individuals who speak and understand, but do not read and write, the language in which the consent discussion is conducted) will have the contents of the document explained to them by a trained study staff member; such individuals can be enrolled by 'making their mark' or thumbprint on the consent document.

Potential participants will have the opportunity to ask questions of the site investigator or delegate, and to discuss participation with their family and/or friends or think about the study prior to deciding whether to participate. A copy of the signed informed consent document will be given to the participant for his/her records.

